4.2.1.2. MTD and RP2D

MTD is defined as maximum tolerated dose, which is the highest dose-level at which <1 out of 6 patients experiences DLT.

The RP2D for a given combination arm is defined as the dose level at which no more than one patient with dose-limiting toxicity (DLT) is observed among six patients for each combination.

4.2.1.3. Sample size justification

The sample size for this study was determined by clinical rather than statistical considerations. With cohort sizes of three to six patients, if the true underlying rates of DLT are 0.1, 0.2, 0.3, 0.4, and 0.5, there will be a 91%, 71%, 49%, 31%, and 17% chance, respectively, of escalating to the next full dose.

4.2.2. Phase 2

The Phase 2 portion of this study will use an estimation approach for PFS-6. For each of the study arms, with a sample size of 30, the lower bound of the two-sided 80% confidence interval, using the exact binomial method using a projected PFS-6 of 20%, will be greater than 10%. This provides meaningful information for further clinical evaluation.

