Initially, 6 patients will be enrolled into a safety cohort for each study arm. The 6-patient safety cohort will be evaluated for the occurrence of DLTs during the first 28 days of combination treatment. For patient in Arm A during the run-in period with BBI608 monotherapy, the same DLT rules as for the combination therapy will apply. Enrollment will be held if ≥ 2 patients are unable to undergo resection due to DLTs. Enrollment will also be held if ≥ 2 patients have an unexpected surgical complication.

For a given arm, if ≥ 2 out of 6 patients experience a DLT, then the BBI608 dose will be reduced for all patients in that arm to the next lower dose level of 240mg twice daily. Furthermore, an additional 6-patient safety cohort in that study arm will be enrolled at the reduced dose-level and evaluated for DLT as described below.

Recommended Phase 2 Dose (RP2D) will be defined as the dose-level evaluated at which ≤ 1 of 6 patients per cohort experiences a DLT.

An additional 24 patients may be enrolled at RP2D in each arm.

For both study arms, cycle length will be 28 days. Combination-therapy cycles will consist of BBI608 administration daily for 28 days and TMZ administration on days 1-5 of each cycle.

Tumor assessments using RANO criteria will be performed every eight weeks from the initiation of combination therapy with BBI608 and TMZ, or otherwise as clinically indicated.

Number of Subjects with DLT at a Given Dose Level for a Given Study Arm	Dose De-escalation Decision Rule
≤ 1 out of 6	This dose level will be considered RP2D for the combination regimen (BBI608+TMZ)
≥ 2 out of 6	Initial dose level will be reduced to a dose chosen by the Investigator and BBI medical monitor. Six (6) additional subjects will be entered at this lower dose level and evaluated for DLT over the first 28 days of combination therapy.

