4.4 Criteria for Dose Escalation and Determination of Dose-Limiting Toxicity

Dose-Limiting Toxicity (DLT) will be evaluated separately in each study arm. Patients evaluable for DLT assessment are defined as having been exposed to at least 28 days of continuous daily administration of BBI608 in combination with TMZ (i.e. DLT evaluation period starts from the first administration of TMZ), or having had a protocol-defined DLT at any time within this period. Based on the tolerability and safety of evaluable patients, enrollment of additional patients will occur according to criteria described below:

- If ≤ 1 treated patients experience a BBI608-related DLT (defined below) by Day 28 of Cycle 1 of combination therapy with TMZ, then additional patients will be enrolled at this BBI608 dose into the RP2D expansion cohort.
- If ≥ 2 treated patients at a dose level experience a BBI608-related DLT by Day 28 of Cycle 1, patient enrollment into this BBI608 dose level cohort will stop and the BBI608 dose will be reduced to the next lower dose level of 240mg twice daily. An additional 6-patient safety cohort will be enrolled at the reduced dose-level and evaluated for DLT.
- RP2D of BBI608 with TMZ will be defined as the dose level at which no more than one patient with DLT is observed among six patients.

The BBI medical Monitor and Principal Investigator will review all significant BBI608-related toxicities to determine whether the initial BBI608 dose (480 mg twice daily) requires adjustment. Lower BBI608 doses may be assigned after agreement between the BBI Medical Monitor and the Principal Investigator.

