For patients in Arm A during the run-in period with BBI608 monotherapy, the same DLT rules as for the combination therapy will apply. Enrollment will be held if ≥ 2 of 6 patients are unable to undergo resection due to DLTs. Enrollment will also be held if ≥ 2 of 6 patients have an unexpected surgical complication.

Initial enrollment will be to a 6-patient safety cohort in each arm. These patients will be evaluated for the occurrence of DLT during the first 28 days of combination treatment with BBI608 and TMZ. If DLT is observed in ≥ 2 of 6 patients evaluable for DLT, the initial dose of BBI608 for all patients in that arm will be reduced to the next lower dose level of 240mg twice daily, and an additional 6-patient safety cohort will be enrolled at that dose-level and evaluated for DLT as above. Enrollment will continue at a dose-level at which ≤ 1 of 6 patients experiences DLT. Dose modification is allowed according to the standard schedule for BBI608.

Cycles of therapy will consist of the patient taking BBI608 daily in combination therapy for 28 days. Tumor assessments will be performed every two cycles (eight weeks), or as otherwise clinically indicated.

The RP2D is defined as the dose level at which no more than one patient with DLT is observed among six patients. Once the RP2D has been reached for a given arm based on

DLT assessment rules outlined above, up to 24 additional evaluable patients may be enrolled at RP2D.

It is expected that up to 30 patients (including those enrolled to the DLT evaluation cohorts) will be enrolled in each arm.

Phase II

In both Phase Ib and Phase II, a study cycle will consist of 28 days of daily administration of BBI608 and TMZ administration on days 1-5 of each cycle. Pharmacokinetic (PK) and pharmacodynamic assessments will be performed in the first cycle only. Safety and tolerability of BBI608 in combination with TMZ will be assessed for the duration of the study treatment and for 30 days after the last dose of BBI608. Evaluation of anti-tumor activity of BBI608 in combination with TMZ will be performed at 8-week intervals while patients remain on study according to RANO.

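### The Phase Ib probabilities in the SAP (91/71/49/31/17%) belong to a 3+3 escalation; under this trial's six-patient rule they are 89/66/42/23/11%

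*SAP*

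**What the plan says.** SAP section 4.2.1.3 first states that the sample size rests on clinical, not statistical, considerations. It then gives operating characteristics. The sentence opens "With cohort sizes of three to six patients" and takes five assumed DLT rates, from 0.1 to 0.5 in steps of 0.1. Its result for these rates is that "there will be a 91%, 71%, 49%, 31%, and 17% chance, respectively, of escalating to the next full dose".

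The design described elsewhere is different:

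- **Cohort size.** SAP section 2.1: "Initial enrollment will be to a 6-patient safety cohort in each arm". Protocol section 4.1 agrees: "Initially, 6 patients will be enrolled into a safety cohort for each study arm". Protocol section 4.4 evaluates DLTs separately by arm.
- **Keeping the dose.** SAP section 4.2.1.2 has the RP2D "defined as the dose level at which no more than one patient with dose-limiting toxicity (DLT) is observed among six patients". Protocol section 4.4 gives the same criterion.
- **Reducing the dose.** With two or more DLTs among six, the BBI608 dose goes down and six further patients are enrolled (SAP sections 2.1 and 4.2.1.1; Protocol sections 4.1 and 4.4).
- **Dose levels.** The schedule in SAP section 4.2.1.1 starts at 480 mg twice daily, and every other level listed is lower.

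**The concern.** The sentence speaks of cohorts of three to six and of moving up to a next dose. Neither feature exists here: there is no three-patient stage, no expansion from three to six, and no BBI608 level above the starting one. The permitted increase in temozolomide is a step within a patient after at least one completed cycle, not a cohort decision. The percentages therefore looked as if they had come from another design.

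What is at stake is an accurate account of how strict the Phase Ib rule is. A reader of the SAP, or of a study report that repeats the sentence, would think a toxic starting dose more likely to be retained, and a dose reduction less likely, than the trial's own rule implies. Neither document gives any other probabilities for Phase Ib; Protocol section 10.2 addresses PFS-6 only.

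**Working it through.** **Inputs.** True DLT rates p = 0.1, 0.2, 0.3, 0.4, 0.5 and the stated percentages, from SAP section 4.2.1.3. Cohort of six, dose kept at one DLT or fewer and reduced at two or more, from SAP sections 2.1, 4.2.1.1 and 4.2.1.2 and Protocol sections 4.1 and 4.4.

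**Step 1: reproduce the SAP's figures.** A 3+3 passes a dose with 0 of 3 DLTs, or with 1 of 3 followed by 0 of 3:

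P(pass) = (1−p)³ + 3p(1−p)² × (1−p)³

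For p = 0.3: 0.343 + 0.441 × 0.343 = 0.4943. All five stated values are recovered on rounding (table below).

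**Step 2: look for another rule that would give them.** At p = 0.1 (stated 91%):

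- at most 1 of 3: 97.2%
- at most 1 of 4: 94.8%
- at most 1 of 5: 91.9%
- at most 2 of 6: 98.4%
- 0 of 6: 53.1%
- both arms passing at most 1 of 6: 78.5%

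The nearest, at most 1 of 5, gives 91.9, 73.7, 52.8, 33.7 and 18.8% across the five rates and matches none of the stated values. Of the rules tried, only the 3+3 fits.

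**Step 3: apply the trial's own rule.**

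P(keep) = P(X ≤ 1 | n = 6) = (1−p)⁶ + 6p(1−p)⁵

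For p = 0.3: 0.1176 + 0.3025 = 0.4202.

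| True DLT rate | SAP states | 3+3 | Keep dose (≤1 of 6) | Reduce dose (≥2 of 6) | 3+3 minus keep (points) |
|---|---|---|---|---|---|
| 0.1 | 91% | 90.6% | 88.6% | 11.4% | 2.0 |
| 0.2 | 71% | 70.9% | 65.5% | 34.5% | 5.3 |
| 0.3 | 49% | 49.4% | 42.0% | 58.0% | 7.4 |
| 0.4 | 31% | 30.9% | 23.3% | 76.7% | 7.6 |
| 0.5 | 17% | 17.2% | 10.9% | 89.1% | 6.3 |

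Measured from the rounded figures as printed, the excess is 2.4, 5.5, 7.0, 7.7 and 6.1 points. At p = 0.5 the ratio is 17/10.9 = 1.56.

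**Step 4: account for the gap.** The two rules differ on one path only. A 3+3 passes on 0 of 3 without treating a second three, whereas the six-patient rule fails if two or more of the second three have a DLT. That path has probability (1−p)³ × [3p²(1−p) + p³]. At p = 0.3 it is 0.343 × 0.216 = 0.0741, which is the 7.4 points in the table. The gap is therefore positive at every rate: the SAP's figures always favour keeping the dose.

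**The case against.** The case against acting concerns consequence, not arithmetic.

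- **Nothing depends on the percentages.** The SAP says the sample size is clinical. The cohort size, the one-or-fewer and two-or-more rules and the DLT analysis (listings only, SAP section 8.2.2.1) are the same whichever figures are printed. This stands and limits the urgency.
- **They guide no remaining decision.** They appear only in the SAP, which is not among the documents listed for IRB approval in Protocol section 12.1. SAP section 8.1.1 records that the sponsor ended all follow-up after 29 June 2018, so planning a second cohort is not a live use. This also stands; the reason to correct the sentence is accurate reporting of the design.
- **The binomial figures are not the whole decision process.** They leave out the Arm A holds for run-in DLTs and surgical complications, and the provision in Protocol section 4.4 for the medical monitor and investigator to agree lower doses. That is true, so the figures should be labelled as probabilities under the numeric rule. None of these features turns the design into a 3+3.
- **A failing cohort may close before six.** Protocol section 4.4 stops enrolment at a dose level once two DLTs occur. This does not alter the probability of at most one DLT in six.
- **The arithmetic is right for the rule it describes.** Agreed. The fault is that this rule is not the trial's.

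**Conclusion.** The concern holds. SAP section 4.2.1.3 gives the operating characteristics of a 3+3 escalation for a trial that uses a six-patient cohort with de-escalation only. Under the trial's numeric rule the chance of retaining the tested dose as RP2D is 89, 66, 42, 23 and 11%, against the stated 91, 71, 49, 31 and 17%. The escalation outcome to which the stated figures are attached cannot occur.

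The calculation assumes six DLT-evaluable patients, independent DLTs with a common rate, and one arm at one dose level. Replacement of non-evaluable patients, which Protocol sections 4.5 and 11.3 allow, keeps the denominator at six. The error should be corrected, but it changes no patient's treatment, no estimate and no interval.

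**What to change.** Replace the second sentence of SAP section 4.2.1.3 with wording such as:

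> For each arm, with six DLT-evaluable patients and true DLT rates of 0.1, 0.2, 0.3, 0.4 and 0.5, the probability under the numeric rule of at most one DLT (dose accepted as RP2D) is 89%, 66%, 42%, 23% and 11%. The probability of two or more DLTs (dose reduced and a further six patients enrolled) is 11%, 34%, 58%, 77% and 89%. These figures assume independent DLTs and do not include the Arm A enrolment holds or reductions agreed at the medical monitor's discretion.

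Delete the references to cohorts of three and to escalation.

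The wording deliberately does not say how the lower dose is set, because the documents disagree. SAP section 2.1 and the text of Protocol sections 4.1 and 4.4 name 240 mg twice daily, while the decision tables in Protocol section 4.1 and SAP section 4.2.1.1 leave it to the investigator and the medical monitor. Those passages need to be reconciled separately.

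The cost is one rewritten statement in the SAP. The design, decision rule and analyses are untouched; the printed figures become slightly less favourable.

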5. INTERIM ANALYSES

No formal interim analyses are planned for this study.

6. ANALYSIS SETS

6.1. Full Analysis Set

The full analysis set (FAS) includes all patients who received at least one dose of any study drug

6.2. PK Analysis Set

The PK analysis set will include all patients from Phase 1b/DLT assessment cohorts who received at least one dose of BBI608 and have at least one quantifiable concentration.

6.3. PD/Biomarker Analysis Set

The PD/Biomarker analysis population is defined as all patients treated and have at least one of the PD/Biomarkers evaluated (including both the patients with only pre-treatment data and those with both pre- and/or post-treatment data).

7. DATA HANDLING

7.1. Methods for Handling Missing Dates

All analyses and descriptive summaries will be based on the observed data. Except for the data otherwise specified in the language below, missing data will not be imputed or “carried forward”. For the subject data listings, no imputation of incomplete dates will be applied. The listings will present the incomplete dates without any change.

Missing or Partial Death Dates

- If the entire date is missing, the death date will be imputed as the day after the date of last contact.
- If the day or both day and month is missing, the death date will be imputed to the maximum of the full (non-imputed) day after the date of last contact and the following:
 - If day is missing, day will be 1st of the month
 - If both day and month are missing, death month and day will be January 1st.

Date of Last Dose of All Study Drugs

No imputation will be done for first dose date. Date of last dose of study drug, if unknown or partially unknown, will be imputed as follows:

- If the last date of study drug is completely missing and the End of Treatment eCRF page has not been completed and no death date has been entered, the patient should be considered ongoing and the cutoff date for the analysis should be used as the last dosing date.

- If the last date of study drug is completely or partially missing and there is EITHER a completed End of Treatment eCRF page OR a death date available (within the data cutoff date), then impute this date as the last dose date:
 - = 31DECYYYY, if only Year is available and Year < Year of min (EOT date, death date)
 - = Last day of the month, if both Year and Month are available and Year = Year of min (EOT date, death date) and Month < Month of min (EOT date, death date)
 - = min (EOT date, death date), for all other cases.

Missing Dates in Adverse Events/Concomitant Therapies

Dates missing the day or both the day and month of the year will adhere to the following conventions:

- The missing day of onset of an AE or start date of a therapy will be set to:
 - first day of the month that the event occurred, if the onset yyyy-mm is after the yyyy-mm of first study treatment
 - the day of the first study treatment, if the onset yyyy-mm is the same as yyyy-mm of the first study treatment
 - the date of informed consent, if the onset yyyy-mm is before the yyyy-mm of the first treatment
- The missing day of resolution of an AE or end date of a therapy will be set to:
 - the last day of the month of the occurrence. If the subject died in the same month, then set the imputed date as the death date
- If the onset date of an AE or start date of a therapy is missing both the day and month, the onset date will be set to:
 - January 1 of the year of onset, if the onset year is after the year of the first study treatment
 - the date of the first treatment, if the onset year is the same as the year of the first study treatment
 - the date of informed consent, if the onset year is before the year of the first treatment
- If the resolution date of an AE or end date of a therapy is missing both the day and month, the date will be set to:
 - December 31 of the year of occurrence. If the subject died in the same year, then set the imputed date as the death date

- If date is completely missing, then no imputation will be done and the event will be considered as treatment emergent (for AEs) or concomitant (for medications) unless the end date rules out the possibility.

Missing Efficacy Endpoints

For primary and secondary efficacy analyses no values will be imputed for missing data. For time to event endpoints, non-event observations will be censored and for ORR/DCR, patients with no post-baseline tumor evaluations or missing baseline tumor evaluation will be counted as non-responders.

Missing Age

If age is missing, age will be computed from birth date to the date of Informed Consent, as $(\text{Date of Informed Consent} - \text{Date of Birth} + 1) / 365.25$ round down to the nearest integer.

- If birth date is missing day, day will be set to 15th to minimize bias
- If missing both month and day, birth date will be set to July 1 of the birth year

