The duration of follow-up is defined as time from the date of first dose of study treatment to the death or last known visit. If a subject dies, the duration is equal to date of death minus study start + 1 with censor variable =1 (censored for follow up). If a subject is alive, the duration is equal to the date subject last known to be alive minus study start + 1 with censor variable=0 (event for follow up).

Extent of Exposure

Exposure may be summarized (overall and by period for Arm A subjects) as dose received (cumulative dose or actual dose intensity) or as dose received relative to intended dose (relative dose [RD], or relative dose intensity [RDI]), or both.

The information that will be summarized depends on how the study drug is dosed (e.g., infusion cyclical, oral daily, oral cyclical).

In what follows “time unit” can be e.g., weeks or days.

Drug accountability will be summarized in a listing.

Intended treatment duration = intended end of treatment date – date of first dose of study drug +1, where the intended end of treatment date is (start date of last cycle + intended cycle duration – 1 day) for each treatment arm

- For BBI608, intended cycle duration= $\max\{28, \text{date of last dose of the cycle} - \text{date of first dose of the cycle} + 1\}$
- For BBI608 in pre-surgical period for Arm A patients, intended cycle duration= surgical procedure date – first dose date + 0.5. Subjects in Arm A took BBI608 in the morning of the surgical procedure and thus took a half day’s dose of BBI608.
- For cyclic combination drug TMZ, intended cycle duration=5 days

Actual treatment duration = actual end of treatment date – date of first dose of study drug +1,

- For BBI608 and TMZ, actual end of treatment date is last dosing date

Cumulative dose in a period (for Arm A subjects), cycle, or overall for BBI608 is the sum of the actual doses received in a period or cycle or overall, respectively. Cumulative dose overall for TMZ is the sum of the actual doses received overall.

Actual Dose Intensity [DI]

- For Arm A subjects: By period actual DI (*dose unit/week*) = [cumulative dose in the period]/[intended period duration in weeks]
- By cycle actual DI (*dose unit/week*) = [cumulative dose in cycle] / [intended cycle duration in *weeks*].
- Overall actual DI (*dose unit/week*) = [overall cumulative dose] / [intended treatment duration in *weeks*].

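### A last-dose date with known month and year but no day is imputed outside its recorded month when the EOT or death date falls in a later calendar year

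*SAP*

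**What the plan says.** SAP section 7.1, under the date of last dose of all study drugs, covers a last-dose date that is partly or wholly missing when there is a completed end of treatment page or a death date. The reference date is the earlier of the EOT date and the death date. There are three branches:

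1. Year-only branch: "31DECYYYY, if only Year is available and Year < Year of min (EOT date, death date").
2. Month-end branch: "Last day of the month, if both Year and Month are available and Year = Year of min (EOT date, death date) and Month < Month", where the second month is that of the reference date.
3. Catch-all branch: "min (EOT date, death date), for all other cases".

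The result is used in three places:

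- **Exposure (SAP 8.2.1).** "For BBI608 and TMZ, actual end of treatment date is last dosing date", so the imputed date closes actual treatment duration.
- **TEAEs (SAP 8.2.4.1).** The window runs to 30 days after the last dose. For this purpose the last dose is the later of what the drug administration record and the end of treatment CRF show.
- **Deaths (SAP 8.2.4.1).** Deaths are summarized if they fall within 30 days of the last dose of any study treatment.

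**The concern.** The second branch compares months only within one calendar year. When the recorded month lies in the year before the reference date, the rule discards the month and assigns a date that the record itself rules out. A site that writes only the year gets 31 December of that year; a site that writes the year and month gets a later date. More information gives a less accurate answer.

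In this gap the error always runs toward a later last dose. What is at stake is the exposure summary and, under conditions set out below, which adverse events and deaths count as falling within 30 days of treatment.

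**Working it through.** The plan states no figure on this point, so the check is one of date logic. All dates below are assumed for illustration; none comes from the documents. Let R be the earlier of the EOT and death dates.

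**Step 1: which branch applies.** Take November 2016 recorded with the day missing, and R = 5 January 2017.

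- Branch 1 fails, because more than the year is known.
- Branch 2 fails, because 2016 is not 2017. Relaxing the year test alone would not help: November is month 11 and January month 1, so the month test fails too.
- Branch 3 applies and gives 5 January 2017.

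The latest date consistent with the record is 30 November 2016. The excess is 31 days (December) + 5 days (January) = **36 days**, a minimum because the true day may be earlier in November. A record of 2016 alone would give 31 December 2016, five days before the date that the fuller record receives.

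**Step 2: other cases.** Each was run through the three branches as written, and again with branch 2 changed to compare year-month with year-month.

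| Recorded | R | As written | Year-month comparison | Excess (days) |
|---|---|---|---|---|
| Dec 2017 | 15 Jan 2018 | 15 Jan 2018 | 31 Dec 2017 | 15 |
| Nov 2017 | 15 Jan 2018 | 15 Jan 2018 | 30 Nov 2017 | 46 |
| Nov 2017 | 15 Feb 2018 | 15 Feb 2018 | 30 Nov 2017 | 77 |
| Sep 2017 | 15 Nov 2017 | 30 Sep 2017 | 30 Sep 2017 | 0 |
| Jan 2018 | 15 Jan 2018 | 15 Jan 2018 | 15 Jan 2018 | 0 |
| 2017 only | 15 Feb 2018 | 31 Dec 2017 | 31 Dec 2017 | 0 |
| nothing | 15 Feb 2018 | 15 Feb 2018 | 15 Feb 2018 | 0 |

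The two versions were then compared for recorded months one to three months before every R from 9 March 2017 (the date of protocol Amendment 3) to 29 June 2018 (the end of follow-up in SAP 8.1.1). They differed only when the recorded year preceded the year of R. The excess in those cases ranged from 1 to 92 days.

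**Step 3: exposure.** Actual treatment duration = last dosing date − first dose date + 1. Assume a first dose on 1 September 2017, November 2017 recorded, and R = 15 January 2018.

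- Ending 30 November: 30 + 31 + 30 = 91 days.
- As written: 91 + 31 + 15 = 137 days.
- Overstatement: 137/91 − 1 = 51%.

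If the imputed date also serves as the last dose of the final BBI608 cycle, the intended cycle duration grows. With that cycle assumed to start on 1 November 2017, it becomes max{28, 30 + 31 + 15} = 76 days instead of max{28, 30} = 30. Cumulative dose is not changed directly, so dose intensity, relative dose and compliance would fall. The SAP does not say whether the imputed date is used there.

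**Step 4: the 30-day windows.** In the Step 1 example the TEAE window would end on 4 February 2017 (5 January + 30 days) instead of 30 December 2016 (30 November + 30 days), but only if the imputed date decides the window. Under the later-of rule there are three situations:

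- *The CRF contributes the EOT date itself.* The window already runs from 5 January 2017 and the imputation adds nothing.
- *The CRF holds a separate, earlier last-dose date.* The imputed date wins and the window lengthens.
- *Only a death date exists.* The last dose is set to the day of death, so events up to death fall inside the window. The death also counts as within 30 days of the last dose. With November 2017 recorded and death on 15 January 2018, the last dose was at least 46 days before death, so the record excludes that classification.

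**The case against.** The best case on the other side concerns consequences and scope, since the gap in the branches is plain on the page and no other section closes it.

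- **Scope.** A reader might infer that exposure and the safety windows are overstated whenever treatment stops across a year end. The documents do not support that. A complete date is never imputed, and a year-only date gets 31 December. The gap needs the day missing, month and year both present, and a reference date in a later calendar year.
- **TEAE window.** A reader might infer that the window always lengthens. It does not, because of the later-of rule in SAP 8.2.4.1. The documents do not show which CRF field feeds that rule. If its definition of last dose carries over to the death summary, the same condition applies there.
- **Size.** Protocol 5.7.1 says that in most cases the last dose and the date off active study coincide. That date is not shown to be the eCRF EOT date, but if the two are close, the usual error is short. Nothing shows that a record with a 36-day gap exists.
- **Efficacy.** PFS and OS do not end on the last-dose date. Study drug end dates can feed the date of last contact (SAP Appendix 1.2), but only as complete, non-imputed dates. The study has no hypothesis testing.
- **Direction.** Counting more events as treatment-emergent is the cautious direction, and the SAP takes it for wholly missing AE dates.

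All of this stands as a limit on impact. None of it justifies assigning a last dose outside the recorded month, and the effect on actual treatment duration does not depend on the later-of rule.

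**Conclusion.** The rule is wrong as written for one narrow class of record: last-dose month and year known, day missing, and the earlier of the EOT and death dates in a later calendar year. Actual treatment duration is overstated in every such case. The shift is at least 36 days in the Step 1 example, and 1 to 92 days when the recorded month is one to three months before the reference date. These sizes rest on assumed dates.

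The effect on the TEAE and death windows is conditional on what the end of treatment CRF supplies. PFS and OS are not affected. The number of patients concerned is not given and is probably small with about 30 per arm, so this is a minor correction with no bearing on the design or the primary endpoint.

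**What to change.** Reword the condition of the second branch in SAP 7.1 so that the last day of the recorded month is used if Year and Month are both available and YYYY-MM < YYYY-MM of min (EOT date, death date). Leave the other two branches unchanged. The AE and concomitant therapy start-date rules in the same section already compare year-month with year-month, so the form is not new to the plan.

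It would also help to state in SAP 8.2.4.1 which end of treatment CRF field enters the later-of rule, and whether that definition of last dose applies to the 30-day death count.

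The cost is one line of SAP text and the matching line of code. In the cases checked with year and month known, only those with an earlier recorded year changed; the year-only, wholly missing and same-month cases gave the same date as before.
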